1.6.2 Specific Objectives

1. To understand the perspectives of stakeholders (school teachers, administrators, parents, community leaders and students) on a school-based FA training (YoFA) program among SSC.

Hypothesis 1: The perspectives of stakeholders like school administrators, teachers, parents, community leaders, and school children needs to be understood to design a comprehensive YoFA program

2. To assess school children's Knowledge, Attitudes (willingness to) and Practices (self-efficacy) (KAP) on trauma/injury FA via the built YoFA training to stop LTBs.

Hypothesis 2: School children have limited knowledge, self-efficacy and practices regarding trauma/injury FA

3. To evaluate the effectiveness and usability of the YoFA training program for SSC to respond to LTBs safely and promptly in their environs.

Hypothesis 3: The YoFA training Program is effective in improving the KAP of SSC and it is usable within the school and community setting.

4. To determine the barriers associated with implementing the YoFA program among early SSC in the Fako Division.

Hypothesis 4: There exist some barrier/challenges in implementing a YoFA training

program in secondary schools.

CHAPTER TWO

LITERATURE REVIEW

It is important to understand some aspects regarding first aid training for children in schools. Here, we will be highlighting the relevance of Advanced Trauma Life Support concepts, the injury burden among school children, the qualifications of potential educators, and the appropriateness of school-based training. There is a clear consensus on the necessity and benefits of teaching first aid in schools, as it equips children with essential life skills, enhances their confidence, and promotes a safer environment. Future research should focus on developing effective training programs tailored to this age group, considering the emotional aspects of learning and the varied contexts in which children may need to apply their skills particularly in our setting.

First aid training is an essential aspect of emergency preparedness, particularly for children aged 10 to 14 years. This age group is increasingly exposed to various risks, both in schools and everyday life. Here, we will explore four key areas related to first aid training for children: the concept of Advanced Trauma Life Support (ATLS), the injury burden among school children, potential educators of first aid, and the appropriateness of implementing first aid training in schools.

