3.2 STUDY POPULATION

The qualitative part will include teachers, principals and vice (of the selected schools), parents (whose kids attend the selected schools), regional delegates (of secondary education and public health) and a few community leaders like quarter heads and or chiefs of both the control and the intervention districts of Buea and Tiko.

The cross-sectional survey will involve students in the early secondary school classes (forms 1 to 3) of the selected state secondary schools (SSS) in Buea and Tiko. These classes are chosen because they have most of the children aged 10-14 years which is the age trained in most studies and we believe these ones have just crossed a milestone from the primary school to get to secondary.

The intervention part will also involve the early SSC who take part in the cross-sectional survey before and after the intervention.

The evaluation will involve all the students as well as the stakeholders in both intervention groups who had been interviewed at the start of the study to determine the impact of the YoFA training program and challenges faced. It will also include the students to assess the need for refresher courses on FA for LTB and equally identify challenges faced during the three months prior to the summative evaluation period.

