3.5 SAMPLE SIZE AND SAMPLING

Sample Size Calculation

For the cross-sectional study and Intervention

Assuming an equal number of control and intervention subjects, a prevalence of the outcome in the controls of 0.5, and a prevalence in the intervention group of 0.75 (an absolute increase of 25%)[17] with a power of 80% and 5% error margin, we calculated the sample size needed using STATA.

Estimated sample sizes for a two-sample proportions test Pearson's chi-squared test using STATA

$H_0: p_2 = p_1$ versus $H_a: p_2 \neq p_1$ Study parameters:

```
alpha = 0.0500
power = 0.8000
delta = 0.2500 (difference)
p1 = 0.5000
p2 = 0.7500
```

Estimated sample sizes:

N =	116
N per group =	58

If we assume a 15% drop out rate, we have a sample size of $15\% * 116 = 17.4$ Thus, sample size is $116 + 17.4 = 133.4 \approx 134$

For each group, the sample needed is therefore **N = 67 students. Sampling**

Since this is a crisis area, we will use convenience sampling to choose the Health Areas (HAs) that are secure and geographically accessible (safest) in both HDs. Out of seven (7) and eight (8) HAs in Buea and Tiko HDs respectively, there are 4 accessible HAs in each. Of these, one HA from each HD does not harbour a state secondary school (SSS).

Leaving us with 3 HAs to work with in each HD. Each of these HAs contains 1 SSS but for 1 HA from each District which has 2 SSSs. We would work with all these State schools to ensure that we get students from most of the communities around the schools, thus ensuring the representativeness of our samples. To avoid spill-over, one of the districts will be selected as intervention HD and the other as the control.

Stratified random sampling will be used to select the students for the study from a sampling frame of the list of students in each classroom concerned.

We would use probability proportionate to size to choose the specific number of students to participate in the study per classroom (A, B, and C) for each class.

[figure not shown]

Figure 5: Selection of HAs and Schools for Implementation.

*GHS-Government High School; BGS-Bilingual Grammar School; GTHS Government Technical High School; GBHS government Bilingual High School

For each school distribution of the participants will be as follows:

A) For the Qualitative part:

The qualitative part will be sampled purposively.

Table 2: Number of Participants to be chosen per school for the FGDs

Health District	Schools	FGD Category of Participant	Number per school

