Buea	1-BGS Molyko	Parents (1) Teachers (1) Students (1)	3
	2-GTHS Molyko	Parents (1) Teachers (1) Students (1)	3
Tiko	1-GHS Mutengene	Parents (1) Teachers (1) Students (1)	3
	2-GTHS Ombe	Parents (1) Teachers (1) Students (1)	3
	Total		12

N.B: Each focused group discussion will be comprised of 5 to 8

Table 3: Number of Participants to be chosen per school for the In-depth interviews

Health District	Schools	Category of Participant	Number per school
Buea	3- GHS Bokwango	Parents (2) Teachers (2) School Admin (1) Students (2)	7
	4-GHS Buea Town	Parents (2) Teachers (2) School Admin (1) Students (2)	7
Tiko	1-GHS Mutengene	Parents (2) Teachers (2) School Admin (1) Students (2)	7
	3-GHS Motombolombo	Parents (2) Teachers (2) School Admin (1) Students (2)	7
	Total		28

B) For the Quantitative or intervention phase

To recruit participants and avoid spill over among initially recruited participants, it was more feasible to randomly choose one classroom from among the selected schools from which to train the students. Thus, instead of table 4 below, we will apply table 5.

Table 4: Initial plan of the YoFA training Participants.

Buea	N	Tiko	N
GHS Bokwango	15	GHS Mutengene	15
GHS Bueatown	15	GTHS Ombe	15
BGS Molyko	20	GBHS Tiko	20
GTHS Molyko	20	GHS Motombolombo	20
TOTAL			70

Table 5: Number of students to train on YoFA Program

Intervention group	School Name	Control	School Name
Buea	BGS Molyko	Tiko	GHS Mutengene
Number of Participants	70		70

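### Section 3.5 claims a representative sample from all accessible state schools, but the quantitative phase as planned rests on one school per district

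*Protocol*

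**What the plan says.** Section 3.5 of the protocol counts three usable health areas per district, each with one state secondary school except one area per district with two. That makes four schools per district and eight in all. It continues: "We would work with all these State schools to ensure that we get students from most of the communities around the schools", and says in the same sentence that this makes the samples representative.

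Part B of the same section, on the quantitative or intervention phase, states that to avoid spill-over "it was more feasible to randomly choose one classroom from among the selected schools from which to train the students", and that Table 5 applies instead of Table 4. Table 4 lists eight schools with 15 to 20 pupils each. Table 5 lists BGS Molyko with 70 and GHS Mutengene with 70. Table 6 (section 3.6) plans training and evaluation at these two schools only.

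Section 3.4.1 gives a third count, four state schools across the two districts. Section 3.2 says: "The cross-sectional survey will involve students in the early secondary school classes (forms 1 to 3) of the selected state secondary schools".

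The descriptive aim is objective 2 in section 1.6.2, with Hypothesis 2: "School children have limited knowledge, self-efficacy and practices regarding trauma/injury FA". Its indicator in Table 7 is the baseline KAP scores. The Abstract and the general objectives in section 1.6.1 place the KAP aim in Fako Division.

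**The concern.** How much early secondary pupils know and do about first aid at baseline is a descriptive question, and the answer depends on which schools supply the pupils. The protocol justifies its sample by coverage of all accessible state schools, then drops to two without withdrawing that justification. The reason given for the reduction, spill-over and feasibility, concerns training; a questionnaire answered before any training does not raise it. The limitations in section 4.1 mention DHIS2 reporting and the absence of private schools, but not the reduction to two schools.

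At stake is what objective 2 and Hypothesis 2 can conclude. With one school per district, a high or low baseline may reflect that school, its district, or both, and the data cannot tell these apart. A reader who relies on section 3.5 would take the result to cover pupils across the accessible schools of both districts.

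**Working it through.** **1. The plan's own sample size.** Section 3.5 heads the calculation "For the cross-sectional study and Intervention" and assumes "a prevalence of the outcome in the controls of 0.5", 0.75 in the intervention group, and a test "with a power of 80% and 5% error margin". With a mean proportion of (0.50 + 0.75)/2 = 0.625:

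n per group = [1.96 × √(2 × 0.625 × 0.375) + 0.8416 × √(0.50 × 0.50 + 0.75 × 0.25)]² / 0.25² = (1.342 + 0.557)² / 0.0625 ≈ 57.7, so 58 per group and 116 in total.

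Adding 15% gives 116 + 17.4 = 133.4, rounded to 134, or 67 per group. The stated figures reproduce. The sample size is not at fault here; what is in question is where the pupils come from.

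**2. Schools that supply quantitative data.**

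| Source | Schools | Pupils |
|---|---|---|
| Section 3.5 text | 3 areas, one with 2 schools = 4 per district, 8 in all | – |
| Section 3.4.1 | 4 | – |
| Table 4 (replaced) | 8 | 2 × (15 + 15 + 20 + 20) = 140 |
| Table 5 (applies) | 2 | 70 + 70 = 140 |
| Table 6 | the same 2 | 3 × 25 + 70 = 145 |

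Between Table 4 and Table 5 the number of pupils stays at 140, while six of eight schools drop out.

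**3. Does the reduction reach the baseline survey?** The protocol never says so directly. The inference rests on these points:

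- One sample size serves both the survey and the intervention (section 3.5).
- The intervention pupils are those who take the survey (section 3.2).
- The pre-tests and post-tests of the two groups are meant to supply the baseline for both districts (section 3.3).
- The trained pupils' pretest opens their training session, and the controls are pretested at the start of the intervention (section 3.6).
- Table 5 includes 70 controls who are not trained, so it is more than a training list.
- No survey number is given for any other school.

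**4. Illustration of size.** Take a proportion of 0.5 from 140 pupils in two schools of 70. The ICC is an assumption, since the protocol gives none. For independent pupils the half-width is 1.96 × √(0.25/140) = 8.3 points.

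- Without finite-population correction: variance = (0.25/140) × [1 + 69 × ICC].
- With correction for two of eight schools: variance = (1 − 2/8) × 0.25 × ICC/2 + 0.25 × (1 − ICC)/140.

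The half-width is 1.96 × √variance.

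| ICC | Factor 1 + 69 × ICC | Without correction | With correction |
|---|---|---|---|
| 0.02 | 2.38 | 12.8 points | 11.8 points |
| 0.05 | 4.45 | 17.5 points | 15.7 points |
| 0.10 | 7.90 | 23.3 points | 20.5 points |
| 0.20 | 14.80 | 31.9 points | 27.8 points |

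With one school per district, variation between schools within a district cannot be estimated from the data, so the analysis could not choose among these rows.

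**The case against.** The strongest reply is that Table 5 restricts training only. Both captions (Tables 4 and 5) speak of training, the reason given is the choice of a classroom from which to train, and section 3.6 still seeks authorisation from eight principals and a sampling frame from the various schools. This stands as a caveat: the loss of the other schools from the survey is inferred. It does not outweigh the points under step 3 of the working, in particular the untrained controls in Table 5 and the absence of survey numbers for any other school.

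Several stronger readings are tempting and are not supported:

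- Section 3.2 might be read as promising a survey of all eight schools. It says only the selected schools, which fits two.
- Chapter Four might be read as promising policymakers a baseline KAP level for Fako. It mentions neither Fako nor a baseline level in that connection. Objective 2 itself does not name Fako either; the Abstract and section 1.6.1 do.
- One might say that the plan will report too narrow an interval, or accept or reject Hypothesis 2 wrongly. The protocol plans no interval, threshold or test for that hypothesis, and such detail may sit in an analysis plan that is not shown.
- One might treat Table 4 as a random sample of schools and quote its precision against that of Table 5. The eight are described as all the accessible state schools, so for that population Table 4 would cover every school and carry no between-school sampling error: 1.96 × √(0.25 × (1 − ICC)/140) is about 7 to 8 points over the same ICCs. For Fako as a whole neither table gives a probability sample, because two of the four districts are left out (section 3.1) and health areas are chosen by convenience.

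**Conclusion.** The representativeness statement in section 3.5 is wrong for the quantitative sample as planned. The document carries school counts of eight, four and two, and on the best-supported reading the baseline KAP data come from two schools, one per district. Objective 2 and Hypothesis 2 can then be answered for those two schools only, and school and district effects cannot be separated. The protocol fixes this through its sampling, and no later analysis can undo it.

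The half-widths of about 12 to 28 points (corrected) or 13 to 32 (uncorrected), against about 8 for independent pupils, show the scale of the problem. They rest on assumed ICCs of 0.02 to 0.20, a proportion of 50%, and the two schools being treated as if drawn at random, either from the eight or from a larger set. A reader might infer that this point also invalidates the power calculation or the training comparison. It shows neither: the sample size reproduces, and the point concerns the descriptive objective.

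**What to change.** 1. In section 3.5, delete the representativeness statement for the quantitative sample.
2. Reconcile the school counts in sections 3.4.1 and 3.5 and in the tables, and say explicitly which schools take the baseline questionnaire.
3. Restrict the conclusions on objective 2 and Hypothesis 2 to early secondary pupils of BGS Molyko and GHS Mutengene.
4. Add to section 4.1 that the quantitative data come from one school per district.

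This is a change of wording only; its price is a narrower conclusion.

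A one-time baseline questionnaire at the other six schools of Table 4, before training starts, is optional. It would add (15 + 15 + 20) + (15 + 20 + 20) = 105 pupils, 245 in all. It is not cheap: it needs parental consent through PTA meetings or returned letters, sampling, and travel by data collectors in what the protocol calls a crisis area. Five of the six schools are already in the qualitative part (Tables 2 and 3); GBHS Tiko is not. Even then the claim would reach the eight accessible state schools, not Fako Division.

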skin wound, correctly apply spiral bandage, correctly stop a nose bleed between 7 and 8 years of age and be encouraged to understand other basic skills. By 9-10 years, they should know that they are not to move seriously painful or hurt parts of the body, know the importance of stopping bleeding as fast as possible, know when to refer a victim with a nosebleed, etc. By 11-12 years, they should receive a repeat of what they know and start applying what they were encouraged to know at a younger age e.g., apply a compression bandage, know 3 possible injuries to the motor system (sprain, dislocation, breakage or fracture), know how to recognize an injury to bones, muscles, or joints. By a later age (13 to 14 years), they should be apt to correctly treat a skin wound if there is no clean water or too little. Correctly treat a wound that contains a foreign object. Correctly remove a splinter. Using disinfectant, know when to refer someone with a splinter to the doctor, among others. As the age group increases, what the child needs is mainly a repeat of what they are expected to know or what they were encouraged to know at an earlier age.

E: Encourage K: Know/Know How R: Repeat	Pre-school (3-6 years)	First grade PS (7-8 years)	Second grade PS (9-10 years)	Third grade PS (11-12 years)	First grade SS (13-14 years)	Second grade SS (15-16 years)	Third grade SS (17-18 years)
1. General Knowledge							
The pupils:							
• Know why they must find help as quickly as possible from an adult in an emergency situation	E	K	R	R			
• Know the general emergency number		K	R	R	R		
• Know the six basic principles of first aid			K	R			
• Know what each emergency service does		E	K	R			
Skills							
The pupils can:							
• Wash their hands	K	R	R	R	R	R	R
• Put on disposable gloves		K		K			
• Use the six basic first aid principles when looking after a victim			E	R	R	R	R
• Recognize the emergency services symbols				K			
Attitudes							
The pupils are prepared:							
• To help	E	K	R	R	R	R	R
• To comfort the victim	E	K	R	R	R	R	R
• To ensure their own safety	E	K	R	R	R	R	R
• To fetch an adult	E	K	R	R	R	R	R
The pupils recognize the importance of:							
• Fetching an adult	E	K	R	R			
• Alerting the emergency services		E	K	R			
• The pupils are prepared to touch a person unknown to them	E		R	R	R		
The pupils recognize the importance of:							
• Avoiding infection				K	R	R	R
• Making the victim comfortable				E	K	R	R
5. Skin wound							
Knowledge							
The pupils:							

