3.4 ELIGIBILITY CRITERIA

3.4.1 Inclusion Criteria

For the Quantitative part

- Form one (1) to three (3) students (ages 10 to 14 years) in the four (4) state secondary schools (SSS) in Tiko and Buea health districts who are willing to participate in the study.
- Students officially enrolled in the school for the academic year
- Those students whose parents consent for their children to be part of the study.

For the Qualitative part

- Stakeholders within the educational care system – Principals, community leaders, and parents who consent to be part of the study.
- Students whose parents give parental consent for their children to participate in the study.

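### Section 3.5 holds two unreconciled sampling rules and fixes no form, so the two arms can end up as different school years

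*Protocol*

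**What the plan says.** Eligibility (3.4.1) covers "Form one (1) to three (3) students (ages 10 to 14 years". On allocation, 3.5 states that "one of the districts will be selected as intervention HD and the other as the control".

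Section 3.5 then gives two rules for choosing pupils.

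- **Main sampling text.** "Stratified random sampling will be used to select the students for the study from a sampling frame of the list of students in each classroom". The number per classroom (A, B and C) in each class is set proportionate to size. This rule spreads the sample over the eligible classes.
- **Part B, intervention phase.** For feasibility and to limit spill-over, the plan is to "randomly choose one classroom from among the selected schools from which to train the students". It adds: "Thus, instead of table 4 below, we will apply table 5". Table 5 lists BGS Molyko (intervention, 70 pupils) and GHS Mutengene (control, 70 pupils). It names no classroom and no form.

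Section 3.6 does not settle the matter. Step 1 still draws from a frame covering many classrooms in many schools, and Step 2 has the controls chosen by the procedure already set out. Section 3.11 plans a difference-in-difference analysis, together with tests between the groups. Age is item 2 of the questionnaire, and class is in its header.

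**The concern.** The two rules lead to different samples. Under the first, both arms can span Forms 1 to 3. Under the second, the school year of the trained group is left to chance, and nothing ties the control group to the same year.

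On the protocol's own account, form matters for this subject. The educational pathway in 2.2.3 and Figure 2 grades content by age; for example, "By 11-12 years, they should receive a repeat of what they know and start applying what they were encouraged to know" at a younger age. Pupils in different forms may therefore differ in starting level, in room to improve and in readiness to act.

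The planned analysis protects only part of the comparison. Difference-in-difference cancels a stable level difference between arms. It does not cancel an age-dependent practice or ceiling effect. It also cannot help an outcome that has no pre-training value. Sections 3.6 (Step 3) and 3.7 list several outcomes whose baseline is absent or unclear:

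- use of the taught skills in the three months after training;
- response time, which 1.1.2 places in the training sessions;
- performance in the scenarios.

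A difference in form would enter these directly. A sample holding one form per arm would also not describe Forms 1 to 3.

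**Working it through.** **The plan's own figure.** The protocol gives no probability for a match of forms. Its only calculation in 3.5 is the sample size, with p1 = 0.50, p2 = 0.75, two-sided alpha 0.05 and power 0.80. The pooled two-proportion formula gives 58 per group and 116 in total, as stated. That figure has no bearing on which form is drawn.

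**Inputs for the check**

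- Eligible forms: three (3.4.1).
- Schools: one per arm (3.5, Table 5).
- Classrooms drawn: one per arm. This is an inference from Table 5 and from the control selection in 3.6; the text does not state it.
- Share of classrooms in each form: not given. The reference to classrooms A, B and C for each class is compatible with equal shares, so equal shares are taken as the base assumption and a range is shown.
- The two draws are assumed independent.

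**Formula.** Let a_f and b_f be the shares of classrooms in form f in the two schools. Then P(arms in different forms) = 1 − Σ a_f × b_f.

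**Results**

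| Shares, intervention school | Shares, control school | Calculation | P(different form) |
|---|---|---|---|
| 1/3, 1/3, 1/3 | same | 1 − 3 × (1/3)² | 0.667 |
| 0.40, 0.35, 0.25 | same | 1 − (0.16 + 0.1225 + 0.0625) | 0.655 |
| 0.50, 0.30, 0.20 | same | 1 − (0.25 + 0.09 + 0.04) | 0.62 |
| 0.60, 0.20, 0.20 | same | 1 − (0.36 + 0.04 + 0.04) | 0.56 |
| 0.70, 0.20, 0.10 | same | 1 − (0.49 + 0.04 + 0.01) | 0.46 |
| 0.50, 0.30, 0.20 | 0.20, 0.30, 0.50 | 1 − (0.10 + 0.09 + 0.10) | 0.71 |

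With equal shares, the arms are one form apart with probability 4/9 = 0.444 and two forms apart with probability 2/9 = 0.222.

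**Where the chance reaches one half.** Suppose both schools have a share s in one form and split the rest equally. Setting s² + (1 − s)²/2 = 0.5 gives s × (1.5s − 1) = 0, so s = 2/3. The chance falls below one half only if one form holds more than about two thirds of the classrooms in both schools.

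**If the form is fixed in advance and is the same in both schools,** the probability is 0.

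These are chances of a mismatch. They do not measure the size of any bias, which the protocol gives no data to estimate.

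**The case against.** The strongest reply is that the mismatch is a reading of the plan, not something it states.

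- **One classroom per school is inferred.** On its words, the sentence in part B concerns the pupils to be trained. The switch to Table 5 changes schools and numbers, and the stratified rule is never withdrawn. If that rule applies within the two Table 5 schools, both arms can span Forms 1 to 3. Taken literally, one classroom would also have to supply 70 pupils (Table 5) or 75 (3 × 25, Table 6), and class sizes are not given. This stands. The firm finding is therefore the conflict and the unspecified form.
- **A reader might infer that the arms will more likely than not be different school years.** The documents do not support this as a fact. It needs classroom counts and independent draws that the protocol does not give, and it fails at a 70/20/10 split.
- **A reader might infer that any difference in gain could be due to school year and not to training.** This goes too far. Stable differences cancel in the planned analysis. The controls are not trained, so if older pupils learn more from training, that is effect modification: it limits to whom the result applies. Bias in the change scores needs untrained pupils of different forms to change differently over the study period, and the documents offer no evidence on that.
- **A reader might infer that no adjustment could help.** If each arm held one form and the forms differed, a form term could not be separated from arm. Age, however, is recorded individually and may overlap between forms. The choice of covariates may also be left to the statistical analysis plan.
- **Matching form leaves arm tied to one school in one district.** This stands too, so the gain from the fix is limited.

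The reply does not explain the two conflicting rules, and it does not cover outcomes without a clear baseline. A draw of a single form cannot be undone at the analysis stage.

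**Conclusion.** The point holds in limited form. Section 3.5 contains two sampling rules that do not agree, and it neither names the form nor matches it between arms. If one classroom is drawn per arm, different school years are possible. The chance is about 2/3 with equal classroom shares and independent draws, and about 0.46 to 0.71 over the other assumed splits.

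In that event part of a between-arm difference could reflect age or form. The exposure is greatest for skill use in follow-up, response time and scenario performance. It is smaller for the change in test scores, where only an age-dependent practice or ceiling effect would remain. The result would also not represent Forms 1 to 3. This is an avoidable imbalance that is cheap to remove; it is not proof that the comparison is invalid.

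**What to change.** Reconcile the two parts of 3.5 so that one sampling rule is in force, and state the form or forms to be sampled in each of the two Table 5 schools. Either of these would do:

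1. **Same mix of forms.** Sample Forms 1, 2 and 3 in the same proportions in both schools. Set the mix once and apply it to both, because proportionate-to-size sampling run separately in each school could give different mixes. Include form or age, both already recorded, in the model.
2. **Same single form.** Draw one form at random, use it in both schools, and limit the conclusion to that form.

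The cost is a change of wording in 3.5. Option 1 means gathering pupils from several classes for training and testing. Option 2 narrows the population to which the result applies.

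Neither option separates the training effect from school or district. Section 4.1 does not mention this at present, and it should be added there as a limitation.
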